5.6.2. End of the Treatment-Free Period

- Time to end of the treatment-free period

The time to end of the treatment-free period is defined as time from the visit guselkumab was injected the last time in Study Part 2 to the date of the R0 visit at which re-treatment was to start, irrespective of PASI assessments. No censoring for subjects without re-treatment applies, as only subjects starting re-treatment are included in the analysis. The time to end of the treatment-free period will be computed as:

- Date of R0 visit – Date of last guselkumab injection in Study Part 2.

The time to end of the treatment-free period will be displayed for observed cases in a summary table providing the mean and median time-to-event, by analysis group and overall. No inferential statistics will be provided.

5.6.3. DLQI Assessments

The Dermatology Life Quality Index (DLQI) is a dermatology-specific quality of life instrument

designed to assess the impact of the disease on a subject's quality of life. It is a 10-item questionnaire that, in addition to evaluating overall quality of life, can be used to assess 6 different aspects that may affect quality of life: 1) symptoms and feelings, 2) daily activities, 3) leisure, 4) work or school performance, 5) personal relationships, and 6) treatment.

The DLQI is calculated by summing the score of each question resulting in a maximum of 30 and a minimum of 0. A higher score indicates more severe disease. A score of ≤ 1 indicates no effect at all of disease on subject's health related quality of life.

For a partially answered questionnaire (eg, not all 10 answers in the DLQI questionnaire are available) the following rules will be applied:

1. If one question is left unanswered this will be scored 0 and the scores will be summed and expressed as usual out of a maximum of 30.
2. If two or more questions are left unanswered the questionnaire will not be scored.
3. If question 7 is answered 'yes' this will be scored 3. If question 7 is answered 'no' or 'not relevant' but then either 'a lot' or 'a little' is ticked this will be scored 2 or 1. If it is answered 'no', but the second half is left incomplete, the score will remain 0.

Note: The answer "Not relevant" will be scored 0, as intended by the score developers.

The following endpoints will be evaluated:

- Proportion of subjects who achieve a DLQI score 0/1 and <5 over time

Per analysis group and overall, the proportion of subjects meeting the response criterion will be displayed in a frequency table providing the number and percentage of subjects (NRI analysis). No inferential statistics will be provided. Graphical presentation will be done by means of bar charts.

- Proportion of subjects with DLQI 0/1 or <5 response 24 weeks after start of re-treatment

Only subgroups within analysis groups III to V (total only) will be analyzed. The proportion of subjects showing response within the R24 visit window will be displayed in a frequency table providing the number and percentage of subjects per subgroup (NRI analysis). For all proportions, unstratified two-sided 95% confidence intervals (CIs) according to Clopper-Pearson will be calculated. Subgroups will be compared exploratorily for the NRI analysis using the Chi-square test (without covariate) to test the difference between two subgroups. The 95% confidence interval for the difference will be calculated based on the Wald statistic. Counts and percentages for subjects responding to treatment, along with odds ratio (OR), relative risk (RR) and risk difference (RD), 95% confidence intervals and the nominal p-value for the factor effect 'subgroup' will be provided.

- DLQI values over time

Per analysis group and overall, DLQI values at scheduled study visits and changes from baseline (R0 visit) will be tabulated by descriptive statistics (OC analysis). No inferential statistics will be provided.

Update after the Dry Run Meeting for the first interim analysis: DLQI values by study visit will also be displayed for selected subgroups according to Section 5.8.8.

Update before start of programming for the final week 220 analysis: Values by scheduled study visit and changes from baseline (R0 visit) will also be tabulated by descriptive statistics (OC analysis) for the DLQI item 1 ("Over the last week, how itchy, sore, painful or stinging has your skin been?") for all subjects and the analysis groups (no further subgroups).

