- Proportion of subjects who achieve a PASI 75/90/100 response at weeks 20, 28, 68, 116, 164, and 220 per study group (**1, 2a, 2b, 2c, 3a, and 3b**)
- Time to loss of disease control (absolute PASI score > 5 at any visit) after treatment withdrawal beyond week 68 per study group (**3a and 3b**)
- Proportion of subjects with an absolute PASI score=0 at all of the following visits: weeks 12, 16, 20, and 28 (**study group 1**)
- Change from baseline (week 0) in Dermatology Life Quality Index (DLQI) score at weeks 28, 68, 116, 164, and 220 per study group (**1, 2a, 2b, 2c, 3a, 3b, and 3c**)
- Proportion of subjects who achieve a DLQI score 0/1 and < 5 at weeks 28, 68, 116, 164, and 220 per study group (**1, 2a, 2b, 2c, 3a, 3b, and 3c**)
- Change from baseline (week 0) in affected Body Surface Area (BSA) at weeks 12, 28, 52, 68, 80, 104, 116, 140, 164, 188, 212, and 220 (**all study groups**)
- Change from baseline (week 0) in the Nail Assessment in Psoriasis and Psoriatic Arthritis (NAPPA) score at weeks 28, 68, 116, 164, and 220 among subjects with nail psoriasis at baseline (week 0; **1, 2a, 2b, 2c, 3a, and 3b**)
- Change from baseline (week 0) in the signs and symptoms aggregate scores of the Psoriasis Symptoms and Signs Diary (PSSD) at weeks 28, 68, 116, 164, and 220 (**1, 2a, 2b, 2c, 3a and 3b**)
- Proportion of subjects who achieve a PSSD sign score=0 at week 68 among subjects with a PSSD sign score ≥ 1 at week 28 per study group (**2a, 2b, and 2c**)
- Association between trough serum guselkumab concentration and efficacy or serum biomarker level
- Association between trough serum guselkumab levels at weeks 20, 28, 36, and 68 and achieving a PASI score < 3 at week 68 per study group (**2a and 2b**)
- Proportion of subjects who were re-treated due to loss of disease control (PASI > 5) and regain control of disease (PASI < 3) 24 weeks after start of re-treatment (study groups **2d and 3c**)
- Safety and tolerability with regard to adverse events (AEs) and abnormal laboratory results (**all study groups**).

Refer to Section 9 for evaluations related to these endpoints.

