4.1. Inclusion Criteria

Each potential subject must satisfy all of the following criteria to be enrolled in the study:

1. Male or female with at least 18 years of age.
2. Has a disease duration of plaque psoriasis of either ≤ 2 years or >2 years calculated from date at which first symptoms [plaque] were reported by subject to date of screening visit at screening; approximately 40% subjects must have a disease duration ≤ 2 years.
3. Has moderate-to-severe plaque-psoriasis defined by a) a PASI score >10 or affected BSA $>10\%$
and b) additionally a DLQI score >10 at baseline (week 0).
4. Is a candidate for systemic treatment for psoriasis.

Reproduction-related inclusion criteria

Contraceptive (birth control) use by men or women should be consistent with local regulations regarding the acceptable methods of contraception for those participating in clinical studies.

Typical use failure rates may differ from those when used consistently and correctly. Use should be consistent with local regulations regarding the use of contraceptive methods for subjects in clinical studies.

5. Before first administration of study drug, a woman must be (as defined in [Attachment 5](#)):
 - a. Not of childbearing potential
 - b. Of childbearing potential and practicing a highly effective method of contraception (failure rate of $<1\%$ per year when used consistently and correctly) and agrees to remain on a highly effective method method while receiving study treatment and until 12 weeks after last dose - the end of relevant systemic exposure. Examples of highly effective methods of contraception are located in [Attachment 5](#).
6. A woman of childbearing potential must have a negative urine pregnancy test at baseline and agree to urine pregnancy testing before receiving injections and at safety follow-up.
7. A woman must agree not to donate eggs (ova, oocytes) for the purposes of assisted reproduction during the study and for a period of 12 weeks after receiving the last administration of guselkumab.

8. A male subject must wear a condom when engaging in any activity that allows for passage of ejaculate to another person.
9. A male subject must agree not to donate sperm for the purpose of reproduction during the study and for a minimum 12 weeks after receiving the last dose of study treatment.

10. TB-related inclusion criteria:

Subjects are considered eligible according to the following TB screening criteria:

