4.2.1. Intent-to-Treat Analysis Set (ITT)

For all analyses on efficacy data obtained during the Re-treatment phase, all subjects starting re-treatment (ie, received at least one dose at or after week R0) will be included in the Intent-to-treat (ITT) analysis set.

Note: In the current SAP template the term 'full analysis set' is used. In this SAP the term 'intent-to-treat analysis set' is used instead to match the Clinical Study Protocol. In terms of content, there is no difference between the two names.

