5. STATISTICAL ANALYSES FOR THE RE-TREATMENT PHASE

For the planned statistical analyses of the Re-treatment phase, the following “analysis groups” are defined:

First interim analysis (re-treatment started the latest at the week 116 visit):

Analysis group I: Re-treatment started in Study Part 2, after week 28 and before week 68.

These subjects had to show PASI >5 to enter the Re-treatment phase (study group 2d),

Analysis group II: Re-treatment started at the end of Study Part 2, at week 68.

These subjects had to show PASI ≥ 3 to enter the Re-treatment phase (study group 3c),

Analysis group III: Re-treatment started during Study Part 3, after week 68 until week 116.

These subjects had to show PASI >5 to enter the Re-treatment phase (study group 3c).

Second interim analysis (re-treatment started the latest at the week 164 visit – analysis was not performed):

Analysis group III: Re-treatment started after week 68 until week 116.

Analysis group IV: Re-treatment started after week 116 until week 164.

Final analysis (re-treatment started the latest at the week 220 visit):

Analysis group III: Re-treatment started after week 68 until week 116.

Analysis group IV: Re-treatment started after week 116 until week 164.

Analysis group V: Re-treatment started after week 164.

All summary tables will provide results by analysis group and for the total of the sample in the respective analysis set.

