5.1.4. Baseline and Endpoint

Baseline for the Re-treatment phase is defined as the observation made at the R0 visit.

Endpoint for the Re-treatment phase is defined as the last available post-baseline result within the analysis period after the R0 visit. Results obtained at unscheduled visits are included in this definition and will be considered as the endpoint value if the unscheduled visit result is the last post-baseline result available within the analysis period for the Re-treatment phase.

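### The re-treatment DLQI response at R24 ignores the R0 score, so subjects already at target count as responders and unadjusted subgroup tests can reflect R0 differences

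*SAP*

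**What the plan says.** Re-treatment SAP 5.6.3 lists the "Proportion of subjects with DLQI 0/1 or <5 response 24 weeks after start of re-treatment". On the numerator it says: "The proportion of subjects showing response within the R24 visit window will be displayed in a frequency table". On the population it says: "Only subgroups within analysis groups III to V (total only) will be analyzed". Under 4.2.1 of the same SAP, "all subjects starting re-treatment (ie, received at least one dose at or after week R0) will be included" in the ITT set. Neither place sets a condition on the DLQI score at R0, although 5.1.4 states: "Baseline for the Re-treatment phase is defined as the observation made at the R0 visit".

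Entry to the phase is set by skin score. For analysis group III, section 5 says "These subjects had to show PASI >5 to enter the Re-treatment phase (study group 3c". Groups IV and V fall under the same protocol rule for loss of disease control.

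The analysis uses non-responder imputation, Clopper-Pearson intervals, and a chi-square test with no covariate between subgroups. Odds ratio, relative risk, risk difference and a nominal p-value are reported. The text describes the subjects counted as responding to treatment. Section 5.8.8 includes this endpoint in the subgroup programme.

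**The concern.** The thresholds 0/1 and <5 are carried over from the main study, where they had a built-in meaning. Protocol 4.1 required "additionally a DLQI score >10 at baseline (week 0", so nobody could meet either threshold at week 0, and meeting one later always meant improvement. At R0 that guarantee is gone. Re-treatment after week 68 is triggered by PASI >5, and relapse can be found at a routine 12-weekly visit as well as after a patient reports worsening. A low DLQI at R0 is therefore possible, and nothing excludes it.

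Two things are at stake. The R24 rate may be read as the frequency with which re-treatment brought quality of life to target, when part of it was there beforehand. And two subgroups that do equally well given their R0 status may show different response rates, with a nominal p-value, because they relapsed with different DLQI levels.

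**Working it through.** **1. Can a subject meet the criterion at R0?** For PASI in groups III to V, no: PASI >5 fails every threshold used (0, <=1, <3, <=5). For DLQI, yes: there is no DLQI entry condition.

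**2. Is R0 DLQI taken into account elsewhere?**
- *Inferential.* PASI change (5.6.1) and PSSD change (5.6.6, by disease duration only) get an ANCOVA with the R0 value as covariate. DLQI change gets no inferential analysis. The unadjusted test of the binary endpoint is the only inferential DLQI analysis in this phase.
- *Descriptive.* Proportions over time, DLQI values and changes from R0 are tabulated by analysis group and overall (5.6.3). Up to five pre-R0 visits are added (5.1.1). DLQI values by visit are shown for subgroups B, D and H (5.8.8).
- *Missing.* The final presentation order in 5.8.8 is A, B, M, D, J, E, K, F, L, I, H. No DLQI-by-visit display is planned for A (randomised interval), M (finer disease duration), J (age), E and K (BMI), F (weight) or L (sex). Subgroup I has no comparison. The subgroup characteristics table lists week 0 PASI and BSA, not R0 DLQI. No planned table gives the R24 proportion among subjects not already at target.

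**3. How large could it be?** The SAP states no figure for this endpoint. The number of subjects comes from section 4.5 of the Overall safety SAP: 236 re-treated in all, less 3 before week 68 and 6 at week 68, leaves 227, the figure given there for re-treatment after withdrawal.

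Let q be the share already at target at R0, r1 their R24 rate, and r0 the R24 rate in the others. All three are assumptions. Then

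all-subject rate = q·r1 + (1−q)·r0, and excess over r0 = q·(r1−r0).

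With r1 = 0.95 and r0 = 0.60:

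| q | All-subject rate | Responders already at target at R0 | Subjects left after restriction |
|---|---|---|---|
| 10% | 0.095 + 0.540 = 63.5% | 0.095/0.635 = 15% | 227 × 0.9 ≈ 204 |
| 20% | 0.190 + 0.480 = 67.0% | 28% | 227 × 0.8 ≈ 182 |
| 30% | 0.285 + 0.420 = 70.5% | 40% | 227 × 0.7 ≈ 159 |
| 40% | 0.380 + 0.360 = 74.0% | 51% | 227 × 0.6 ≈ 136 |

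The rate among subjects not yet at target is 60% throughout. With r0 = 0.75 the all-subject rate runs from 77% (q = 10%) to 83% (q = 40%).

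**4. Subgroup comparison.** Give two subgroups the same r1 and r0 but different shares qa and qb. The difference in all-subject rates is (qb−qa)·(r1−r0). Split 227 as 113/114 (an assumption; no document gives a split). With s0 the pooled and s the unpooled standard error, P(p<0.05) ≈ Φ((Δ−1.96·s0)/s) + Φ((−Δ−1.96·s0)/s).

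Worked case: 63.5% vs 70.5%, Δ = 0.070, s0 = 0.0624, s = 0.0623. The first term is Φ(−0.84) = 0.200, the second is 0.001, and the total is about 20%.

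| r1 / r0 | qa vs qb | Rates | Difference | P(p<0.05) |
|---|---|---|---|---|
| 0.95 / 0.60 | 10% vs 30% | 63.5% vs 70.5% | 7.0 points | 20% |
| 0.95 / 0.60 | 10% vs 40% | 63.5% vs 74.0% | 10.5 points | 40% |
| 0.95 / 0.75 | 10% vs 30% | 77.0% vs 81.0% | 4.0 points | 11% |
| 0.95 / 0.75 | 10% vs 40% | 77.0% vs 83.0% | 6.0 points | 20% |
| either | equal | equal | 0 | 5% |

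The two-group calculation does not fit subgroups D (four levels in the final analysis) or E (three levels).

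**The case against.** The strongest reply is that the endpoint is a proportion in a given state at a visit, which is a legitimate quantity and common in this study. The primary endpoint itself is PASI <3 at week 68 in subjects who all had PASI 0 at week 28. On that reading the rejections in step 4 are not false positives, because the R24 proportions do differ. This stands for the proportion itself. It does not cover the word response, or the description of those counted as responding to treatment.

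The plan also gives partial context. Disease duration (B), time of entry (D) and week 68 PASI (H) do get DLQI by visit, and R0 percentages and changes are shown by analysis group. That stands too. The gap is confined to the other tested subgroups and to the missing at-risk proportion.

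The analyses are exploratory, were not planned in the protocol, and carry nominal p-values. No confirmatory conclusion depends on them.

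A reader might go further and infer that the planned rates do overstate the benefit of re-treatment, or that the subgroup tests have an inflated error rate. The documents do not support either. They contain no R0 DLQI distribution, and the direction of the first depends on r1 exceeding r0. The second needs R0 DLQI to differ between subgroups. Fewer subjects can qualify at R0 for 0/1 than for <5, so any effect there should be smaller. A reader might also take the protocol's PSSD endpoint, "Proportion of subjects who achieve a PSSD sign score=0 at week 68 among subjects with a PSSD sign score" of at least 1 at week 28, as proof that the authors recognised this problem. The protocol gives no reason for that restriction. It shows only that a denominator of subjects not already at target has been used in this study.

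**Conclusion.** The point holds as one of definition and labelling. As written, a subject at DLQI 0/1 or <5 at both R0 and R24 is a responder to re-treatment, and the only inferential DLQI comparison in this phase makes no allowance for the R0 score. How much this matters cannot be determined from the documents. Under the assumed inputs the all-subject rate exceeds the at-risk rate by 2 points (q = 10%, r0 = 0.75) to 14 points (q = 40%, r0 = 0.60). Subgroup tests reject 11% to 40% of the time in the unequal cases shown and 5% when R0 shares are equal. These figures illustrate the mechanism and are not estimates for this trial. The weight is that of a cheap improvement to an exploratory analysis.

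**What to change.** In Re-treatment SAP 5.6.3 and 5.8.8:

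- Keep the all-subject R24 proportions, but label them as DLQI status at R24, not as response to treatment.
- Add the R24 proportion with Clopper-Pearson interval, keeping non-responder imputation, among subjects with R0 DLQI >1 (for 0/1) and among subjects with R0 DLQI >=5 (for <5).
- Show, for each subgroup, the number already at target at R0.
- Adjust the subgroup comparisons for R0 DLQI, for example by logistic regression with subgroup and R0 DLQI as terms. Restriction alone is not enough, because subgroups can still differ in R0 DLQI above the threshold.
- State how a missing R0 DLQI is handled. It can arise when two or more items are unanswered, or when prohibited medication has set the value to missing (5.1.8).

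DLQI is scheduled at R0, so no new data are needed. The cost is SAP wording, one flag per criterion and one model. The downsides are smaller denominators that differ between the two criteria, and a restricted rate that still has no control arm and is open to regression to the mean. The Overall safety SAP already describes the final re-treatment analysis in the past tense. If those tables exist, the additions should be reported as post hoc.

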5.6.4. BSA Assessments

One physical measure to define disease severity is to determine how much of the Body Surface Area (BSA) is affected by psoriasis. Involved BSA is calculated by using the palm of the subject's hand as equivalent to 1% of the BSA (rule of palm).

The following endpoint will be evaluated:

- Affected BSA over time

For analysis groups III to V (and overall) only, BSA values at scheduled study visits will be tabulated by descriptive statistics (OC analysis). Changes from baseline (R0 visit) cannot be computed since BSA was not documented at the R0 visit. No inferential statistics will be provided.

5.6.5. NAPPA Assessments

The Nail Assessment in Psoriasis and Psoriatic Arthritis (NAPPA) is an instrument for assessing clinical and patient-reported outcomes in nail psoriasis (Augustin, et al. 2014). It comprises three components:

1. NAPPA-QOL is a 20-item nail-specific quality of life (QoL) questionnaire covering the past week. Signs, stigma and everyday life are rated on a scale from 0 (no suffering) to 4 (high suffering). The NAPPA-QOL global score is computed by averaging all items. In case more than 25% of the items are missing (6 or more items missing), the score is not computed for the respective patient.
2. NAPPA-PBI is a 24-item questionnaire to assess patient-defined needs before and patient-rated benefits after treatment. The answers are given on a scale from 0 to 4. The weighted NAPPA-PBI global score is computed as follows: For score calculation, both "does not apply" and "question unanswered" will be treated as missing values. The global score will be calculated using all items pairs (importance + benefit) for which the patient has given a response other than "does not apply". Each benefit item is multiplied with the respective importance item, and the product is divided by the sum of all importance items. The results are summed up over all items. The resulting global score ranges from 0 (no benefit) to 4 (highest possible benefit). Only if more than 25% of items pairs are unanswered (=7 or more item pairs with missing values), no global score will be calculated.
3. NAPPA-CLIN has been developed from the Nail Psoriasis Severity Index (NAPSI) score, a nail psoriasis-specific score, which in its original version comprises the assessment of matrix and nail bed involvement in every finger and toe by 8 criteria for each nail. The NAPPA-CLIN is a simplified version of the NAPSI which only assesses the least and the worst involved nail of both hands, or both feet, respectively. Score (matrix or bed for hands or feet)) is 0 if the findings are not present, 1 if they are present in 1 quadrant of the nail, 2 if present in 2 quadrants of a nail, 3 if present in 3 quadrants of a nail, and 4 if present in 4 quadrants of a nail:
 - thus, each nail has a matrix score (0-4) and a nail bed score (0-4), and the total nail score is the sum of those 2 individual scores (0-8) for hands or feet;

- sum of the total score of all involved nails is the total NAPPA-CLIN score for that patient at that time for hands or feet;
- thus, the NAPPA-CLIN scores for hands or feet range from 0 to 16 empirically;
- if a matrix score or a nail bed score is missing, the NAPPA-CLIN score is also missing.

The following endpoint will be evaluated:

- NAPPA score over time

For analysis groups III to V (and overall) only, the global scores of NAPPA-QOL, NAPPA-PBI, and NAPPA-CLIN at scheduled study visits and changes from baseline (R0 visit) will be tabulated by descriptive statistics (OC analysis). According to the definition of the global score of NAPPA-PBI, the post-baseline values are already the changes from baseline (there is no baseline value). No inferential statistics will be provided.

